### Other Tasks

Probabilistic Reward Task (PRT) will be conducted outside of the scanner. This task allows us to test the additional hypothesis that perimenopausal depression is characterized by blunted reward learning. During this task, correct identifications of two ambiguous stimuli are differentially rewarded. The task will consist of 300 trials, divided into 3 blocks of 100 trials. Each trial starts with the presentation of a fixation cross for 500 msec followed by a mouthless face. After a delay of 500 msec, either a short mouth (11.5 mm) or a long mouth (13 mm) is presented for 100 msec. Participants will be asked to identify which type of mouth was presented. For each block, the long and short mouths are presented equally often in a pseudorandomized sequence and 40 correct trials are followed by reward feedback immediately after the correct response. An asymmetrical reinforcer ratio will be used in this task, such that for half of the participants, correct identification of the short mouth will be associated with three times more positive feedback (30 of 40) than correct identification of the long mouth (10 of 40). For the other half of the participants, the contingencies will be reversed.

Participants will be paid same-day for the amount earned on the PRT and the MID. Participants will sign a form at that time to confirm they received payment and to confirm the amount they received. The money earned during the PRT and MID will be part of the \$500 compensation.

### **3.2 Primary Study Endpoints**

1. Frontostriatal reactivity to reward during the MID fMRI task
2. Response latency to reward versus non-reward during the MID fMRI task
3. Depressive symptoms

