**Aim 3: To measure dysphoria at baseline and following estradiol administration.** Dysphoria will be assessed at baseline and following estradiol administration. Training associated with this aim will include assessing associations between neural activity and psychological symptoms.

*H3a:* Women with perimenopausal MDD will report a significant reduction in depressive symptoms following estradiol administration, and the degree of symptom improvement will be associated with the change in frontostriatal responsivity to reward.

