**Clinical Assessments**

The Structured Clinical Interview for DSM-IV-TR Axis-I Disorders (SCID) and the Schedule for The SCID1 will be administered at baseline to determine study eligibility. The following standard measures will be administered at baseline, both fMRI sessions, and weekly clinic visits:

- The Positive and Negative Affect Schedule is a 20-item questionnaire that measures both positive affect (PA) and negative affect (NA) and is sensitive to subtle changes in affect over time.
- The Hamilton Rating Scale for Depression (HRSD) is a 21-item researcher-rated standardized scale that assesses depressive symptoms and is widely used as a measure of symptom change over time.
- The Inventory of Depression and Anxiety Symptoms (IDAS) is a 64-item self-report questionnaire that comprehensively assesses anxiety and depression symptoms on 10 subscales. The IDAS has excellent psychometric properties and has been validated for assessing reproductive mood disorders.
- The Mood and Anxiety Symptom Questionnaire - Anhedonic Depression Subscale (MASQ-AD) is a 22-item scale that assesses anhedonia (i.e., loss of interest and low positive affect). MASQ-AD scores have been associated with blunted striatal response to reward in previous studies of patients with depression.
- The Greene Climacteric Scale (GCS) is a 21-item scale that is the gold-standard measure of four domains of climacteric symptoms: vasomotor, somatic, anxiety, and depression.
- The Pittsburgh Sleep Quality Index (PSQI) is a 9-item questionnaire that measures the quality and sleep patterns in older adults. \*This measure will only be administered at the two fMRI sessions.

While the SCID and HAM-D are researcher administered, the other measures will be collected through self-report questionnaires using *Qualtrics* or paper and pencil questionnaires.

Despite the use of exclusion criteria designed to reduce risk to participants, depressive symptoms are monitored closely. Any subject who develops severe depressive symptoms (e.g., suicidal ideation) will be discontinued from the study and offered treatment paid for by the study. If inpatient hospitalization becomes

necessary as a result of the study, UNC Health Care will cover the cost. The following language has been added to the study consent form to reflect this policy:

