#### **4.4.2 Data Collection and Follow-up for Withdrawn Subjects**

Participants who elect to discontinue the hormone protocol or are discontinued for safety reasons will be asked to continue to complete self-report ratings through the end of the proposed study period. However, fMRI exams will not be done if participants discontinue the hormone protocol.

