### 7.2 Statistical Methods

This study has one between-subjects factor (group: MDD versus control) crossed with one within-subjects factor (time: baseline versus estradiol treatment) with the outcome (percent signal changed) assessed in response to the MID task in the structurally defined frontostriatal ROIs, including the nucleus accumbens, caudate, thalamus, frontopolar cortex, and dorsolateral prefrontal cortex. Thus, for a task/ROI combination, there is a 2-by-2 repeated measures design. We will analyze this design using an ROI analysis and mixed models with an unstructured covariance structure. To test whether perimenopausal women with MDD show reduced frontostriatal activity (H1) and motivated behavior (H2) in response to reward at baseline, we will examine group differences in BOLD signal and response latency at baseline. To measure the psychological correlates of the frontostriatal response to reward, we will examine change in depressive symptoms between baseline and post-treatment in MDD relative to controls (H3).

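### Primary endpoint 3 names no scale, score or baseline visit, and section 7.3 leaves out symptom ratings that section 4.4.2 collects from discontinued women

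*Combined protocol and SAP*

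**What the plan says.** Section 3.2 lists "3. Depressive symptoms" and nothing more. In section 2, Aim 3 uses another word for the construct: "Dysphoria will be assessed at baseline and following estradiol administration". H3a, directly below it, and the Study Summary return to depressive symptoms. Section 7.2 compares the change in the MDD group with that in controls. None of these places names an instrument, and the power statement in 7.1 is not tied to one.

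Table 1 schedules the HAM-D (HRSD), IDAS, PANAS, MASQ and GCS at visits 1, 3, 4, 5 and 6. Under Clinical Assessments, the HRSD "is a 21-item researcher-rated standardized scale that assesses depressive symptoms and is widely used as a measure of symptom change over time", and the IDAS "is a 64-item self-report questionnaire that comprehensively assesses anxiety and depression symptoms on 10 subscales". The GCS has a depression domain of its own. On mode of collection: "While the SCID and HAM-D are researcher administered, the other measures will be collected through self-report questionnaires". All women receive the same known regimen (5.3), blinding is not applicable (5.8), and no rater masked to group or visit is described.

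Clinical Assessments and section 4.4.1 discontinue women for severe mood symptoms. Under 4.4.2, women who stop or are discontinued "will be asked to continue to complete self-report ratings through the end of the proposed study period". They are not scanned again, and the HRSD is not mentioned. Section 7.3 then restricts the study analysis to protocol-compliant participants.

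**The concern.** Two things are left open, and both bear on whether the symptom result can be trusted.

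The first is selection. With several scales and no multiplicity rule, the scale, the score and the baseline can all be settled after the data are seen. The word baseline is itself used for two visits. The SCID is given at baseline and Table 1 puts it at visit 1; the first scan is also at baseline and Table 1 puts it at visit 3. Estradiol is first supplied at visit 3, so both visits can serve as the pre-treatment value.

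The second is outcome-related loss. The women most likely to be discontinued for mood are those whose symptoms became severe. Their self-report ratings are to be collected, yet the natural reading of 7.3 excludes them. If the HRSD is the measure, the ratings may not exist at all. If these women are mainly in the MDD group, their removal makes the average change after estradiol look better than it was. The study is meant to supply pilot data for a larger placebo-controlled trial (1.1), so the error would carry forward.

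**Working it through.** **The plan's own figure.** Inputs from 7.1: 20 per group, d = 0.9, power 80%, two groups compared on change scores. Alpha is not stated; I assume 0.05 two-sided. By the normal approximation, power = Φ(d√(n/2) − 1.96) = Φ(0.9 × √10 − 1.96) = Φ(0.886) = 81.2%. The noncentral t with 38 df gives 79.2%. The stated 80% reproduces. So does the total: 40 / (1 − 0.20) = 50. The calculation holds for any one outcome and says nothing about which symptom scale is meant.

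**Choosing the best scale.** If k scales were independent, the chance of at least one p < 0.05 under no true difference is 1 − 0.95^k: 18.5% for k = 4 and 22.6% for k = 5. Scales of this kind are correlated, so I simulated equicorrelated normal change scores (20 per group, no true difference, two-sided t tests, 20,000 runs per setting):

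| Scales | correlation 0.3 | 0.5 | 0.7 |
|---|---|---|---|
| 4 (without PANAS) | 17.6% | 15.6% | 13.4% |
| 5 | 21.1% | 18.6% | 15.0% |

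Only a result favouring the MDD group would support the hypothesis. By symmetry the favourable-direction rate is about half: 13.4% / 2 = 6.7% to 21.1% / 2 = 10.6%, so about 7% to 11%, against 2.5% for one named scale. The free choice between two baseline visits is not in these figures and would add to them.

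**Excluding discontinued women.** The documents give no expected number of mood-related discontinuations, so this is an illustration. Assume 25 MDD women (half of 50), no true change, 20 complete controls, and the m women with the worst change removed:

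| m removed | shift toward improvement (SD) | false improvement within MDD | false advantage of MDD over controls |
|---|---|---|---|
| 1 | 0.08 | 7% | 5% |
| 2 | 0.15 | 14% | 8% |
| 3 | 0.22 | 23% | 12% |
| 5 | 0.34 | 46% | 23% |

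The nominal rate in both right-hand columns is 2.5%. This is a severe case, because the women removed are exactly those with the worst change.

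**What is lost for whom.** Section 4.4.2 continues self-report ratings only, and Clinical Assessments places the HRSD among the researcher-administered measures. Read together, the HRSD ends at discontinuation. That is an inference; no section says it outright. For the IDAS, MASQ-AD, PANAS and GCS the ratings are to be collected, and the loss arises only at analysis, through 7.3.

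**The case against.** The five scales are not equal candidates. By the protocol's own descriptions the PANAS measures affect, the MASQ-AD anhedonia, and the GCS climacteric symptoms with one depression domain. The HRSD is the scale described in terms closest to the endpoint. That is fair, and it is why I give a range starting from four scales and do not count every IDAS subscale, since the IDAS also covers anxiety. But a close description does not designate a primary measure.

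A reader might infer that H3a could be declared met on whichever scale moved. It could not: H3a also requires symptom improvement to be associated with the change in frontostriatal response. The error rates above apply to the group comparison in 7.2, not to H3a as a whole.

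A reader might also infer that symptom data are missing for any woman who worsens. The documents do not support this. Discontinuation for mood follows severe symptoms, current suicidal ideation is already excluded at entry (4.2), and self-report continues afterwards. Only the HRSD would be missing, and only by inference.

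The restriction in 7.3 is explained by the interest in brain function, and women who stop are not rescanned. That justifies it for the imaging endpoints. It does not carry over to a symptom endpoint that needs no scan.

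Finally, participants know they are taking estradiol, so self-report carries expectation as well. The documents therefore give no decisive reason to demote the HRSD; that choice belongs to the sponsor.

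**Conclusion.** The point stands in two parts. Endpoint 3 has no scale, score or unique baseline, and free choice among four or five scales raises the false-positive rate of the 7.2 comparison from 5% to about 13% to 21% two-sided, or from 2.5% to about 7% to 11% in the favourable direction. This rests on an assumed alpha of 0.05, correlations of 0.3 to 0.7 and 20 per group. In addition, 7.3 leaves out symptom ratings that 4.4.2 collects from discontinued women. The direction of that bias is clear if those women are mainly in the MDD group; its size depends on a number that the documents do not give.

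Naming one scale controls selection only. Women chosen for current MDD may improve more than never-ill controls without any estradiol effect, and there is no placebo group. If that difference were d = 0.3 (assumed), a single scale would reject in about 15% of trials; at d = 0.5, in about 34%. The correction should be made, but it does not turn endpoint 3 into evidence of a drug effect.

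**What to change.** - In 3.2, in Aim 3 and H3a, and in 7.2, name one scale and one score as primary before any outcome data are examined. Fix one baseline visit (1 or 3) and make visit 6 the end visit. Use one term for the construct throughout, and list the other scales as supportive.
- A self-report depression score is one option, because 4.4.2 keeps it running after discontinuation; if it comes from the IDAS, the exact score must be named. If the HRSD is chosen, state who rates it and that it continues after discontinuation.
- In 7.3, write an explicit exception: endpoint 3 is analysed in all treated women, using the ratings that 4.4.2 provides for, with the compliant-only analysis as supportive. The association with frontostriatal change remains limited to women with both scans.
- Reconcile the discontinuation wording. Clinical Assessments gives suicidal ideation as an example of what leads to discontinuation, while 4.4.1 and 8.5 call for repeated rating and refer to plans or intent, or to concern about continuing. Sections 4.4.1 and 8.5 also say that the HRSD is given at every visit, but Table 1 shows none at visit 2.

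The cost is wording, with no new visits; a choice of the HRSD would add ratings by staff after discontinuation. The symptom estimate may be slightly less favourable, and whichever scale is named remains unblinded. Keeping all the scales as primary with a Bonferroni correction would cost more: power at d = 0.9 falls from 79% to 59% with four scales or 56% with five.

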### **3.3 Secondary Study Endpoints**

1. Neural connectivity measured during resting-state fMRI

### **3.4 Primary Safety Endpoints**

N/A

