
Adverse Events Related to Combined Hormone Replacement and the Results of the Women's Health Initiative (WHI): The WHI study demonstrated that continuous administration of one form of estrogen (conjugated estrogens) in combination with one form of progesterone (medroxyprogesterone acetate) is associated with an increased risk of dementia, heart attacks, stroke, blood clots, and breast cancer. Estradiol, the form of estrogen that we use in this study, is administered as a sole agent (with the exception of one week's combination with progesterone) and, consequently, we do not expect that it will

pose the increased risks observed with the chronic combination of the conjugated estrogens and medroxyprogesterone administered in the WHI study. Indeed, while the estrogen alone arm of the WHI trial was shown to be associated with an increased risk of stroke, no increased risk of either heart disease or breast cancer was observed. Estrogens may precipitate migraine headaches, and depression has also been reported to occur with the use of estrogens. In general, considering the dose and duration of treatment that we propose to use in this protocol, the risk of developing such side effects is negligible.

**Progesterone:** Progesterone and the synthetic progestins are widely prescribed, with indications including dysfunctional uterine bleeding, endometriosis, mastodynia, galactorrhea, and precocious puberty. Side effects reported in women taking progestins may include breakthrough bleeding, edema, change in weight (increase or decrease), cholestatic jaundice, rash (with or without pruritus), depression, easy fatigue and sedation, lack of initiative, and chloasma. Since progestins are often used in women with antecedent menstrual irregularity, it is not clear whether the breakthrough bleeding represents an effect of the medication or refractoriness to treatment. In the large majority of patients, menstruation occurs predictably following withdrawal of progestins and is usually more regular than in spontaneous cycles. In a recent study, an average dose of 1750 mg of oral micronized progesterone was given to 59 women with PMS for a period of three months and was well tolerated by this sample. The side effects reported on progesterone were lightheadedness, fatigue, forgetfulness, and headaches. These were very mild and caused no dropouts.

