### **4.4 Early Withdrawal of Subjects**

#### **4.4.1 When and How to Withdraw Subjects**

Participants with significant clinical or laboratory abnormalities will be discontinued from the study prior to estrogen administration.

Adverse mood symptoms will be monitored by administering the the Hamilton Rating Scale for Depression (HRSD) at each study visit. **If suicidal thoughts or severe mood symptoms are observed at any period in the medication phase, then the suicide item of the HRSD will be administered on consecutive days for three days. Anyone who expresses suicidal thoughts with plans or intent, or who expresses concern about her ability to continue in the study, will be considered to have severe mood symptoms and be discontinued from the protocol.** In the event of the occurrence of severe mood symptoms, the protocol will be terminated. Should this step prove to be unsuccessful, conventional medication will be prescribed as needed. Although we do not anticipate severe adverse reactions, we have arranged for inpatient hospital admission in the Psychiatry Department if symptoms are otherwise unmanageable.

Any patient experiencing clinically significant side effects such as nausea, hypertension, vomiting or extreme fluid retention from the medication will have the dose titrated to achieve relief of the symptoms. If adequate relief cannot be achieved in this manner, drug treatment will be discontinued.

The determination of when and how to withdrawal subjects will be overseen by the study's principal investigator, co-investigators, and research coordinators and will be reported to the UNC Biomedical IRB.

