### 7.3 Subject Population(s) for Analysis

Given that we are interested in understanding the effect of estradiol on brain function, only data from protocol-compliant participants will be subjected to the study analysis.

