## **8.2 Recording of Adverse Events**

At each contact with the subject, the investigator will seek information on adverse events by specific questioning and, as appropriate, by examination. Information on all adverse events will be recorded immediately in the source document, and also in the appropriate adverse event module of the case report form (CRF). All clearly related signs, symptoms, and abnormal diagnostic procedures results will be recorded in the source document, though will be grouped under one diagnosis.

All adverse events occurring during the study period will be recorded. The clinical course of each event will be followed until resolution, stabilization, or until it has been determined that the study treatment or participation is not the cause. Serious adverse events that are still ongoing at the end of the study period will be followed up to determine the final outcome. Any serious adverse event that occurs after the study period and is considered to be possibly related to the study treatment or study participation will be recorded and reported immediately.

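### Adverse events and discontinuations are recorded, but no planned result reports them by group with an all-treated denominator, and section 7.3 naturally reads as leaving out women whose treatment was stopped for harm

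*Combined protocol and SAP*

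**What the plan says.** The section headed "3.4 Primary Safety Endpoints", the protocol's only place for a safety endpoint, reads N/A. Section 3.2 lists "Depressive symptoms" as the third primary endpoint. Section 7.2 plans analyses of regional brain signal, response latency and change in depressive symptoms, and nothing else. Section 7.3, explaining that the interest is in estradiol's effect on brain function, says "only data from protocol-compliant participants will be subjected to the study analysis". It names no other analysis set.

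Mood worsening is a foreseen harm. Section 1.4 notes that "depression has also been reported to occur with the use of estrogens" and lists depression among reported progestin side effects. Section 4.4.1 says "Adverse mood symptoms will be monitored by administering the the Hamilton Rating Scale for Depression (HRSD) at each study visit". A woman with suicidal plans or intent, or who is concerned about her ability to continue, "will be considered to have severe mood symptoms and be discontinued from the protocol". Drug is also stopped for side effects that cannot be relieved. Section 8.5 repeats these rules. Under section 4.4.2, women who stop are asked to keep completing self-report ratings but are not scanned again.

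On collection, section 8.2 says "All adverse events occurring during the study period will be recorded". Section 8.1 runs the reporting period to 30 days after the last study treatment. Section 8.3 covers reporting to the IRB and FDA, and section 8.6 gives the investigator a regular review of the number and type of serious events.

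**The concern.** Roughly half the women have current major depression, all receive both hormones, and worsening of mood is both a recognised harm and a reason to stop treatment. The only analysis set in the plan is the one these women are least likely to enter. A report that followed section 7 to the letter would give average symptom change in compliant women. It would contain no count of adverse events, no count of women stopped for mood or side effects, and no denominator for either. The protocol presents the study as pilot data for a larger randomised trial (section 1.1) and as help in identifying women likely to benefit from hormone therapy (section 1.5). Readers with either purpose would want the tolerability results.

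**Working it through.** **The plan's own headcount.** Section 7.1 has 20 per group, so 40, plus 10 for attrition: 40 + 10 = 50. As a rate, 10/50 = 20%, and 40/(1 − 0.20) = 50. The figure reproduces. The 80% power statement in the same section concerns group differences in change scores and says nothing about harms.

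**What is collected, and what section 7 does with it.**

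| Data | Where collected | Planned use in section 7 |
|---|---|---|
| Adverse events | 8.1, 8.2 | None |
| Serious adverse events | 8.3; aggregate review in 8.6 | None |
| Discontinuations and reasons | 4.4.1, 8.5 (reported to the IRB) | None |
| HRSD, including suicide item | Table 1, visits 1 and 3 to 6 | At most through change in depressive symptoms, compliant women only (7.2 names no scale) |
| Self-report ratings after discontinuation | 4.4.2 | None stated |

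**Does 7.3 exclude a discontinued woman?** This is an inference.
- If compliant means completing treatment and both scans, she is out.
- If it means adherence to the drug regimen, which is the subject of section 5.5, or obedience to the protocol including its own withdrawal rules, she could be in.
- The brain-function rationale in 7.3 and the missing second scan favour the first reading.
- Under every reading, section 7 contains no table of adverse events or discontinuations. That part of the point does not depend on the definition.

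**How many women?** The documents do not say. If the attrition allowance is met exactly, the number leaving because of harm lies between 0/50 = 0% and 10/50 = 20%.

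**What all-treated tables could show.** For zero events in n women, the upper limit of the exact two-sided 95% interval is 1 − 0.025^(1/n).
- n = 50 (all enrolled, assuming all start estradiol): 1 − 0.025^(1/50) = 7.1%.
- n = 25 (one group, assuming an even split): 1 − 0.025^(1/25) = 13.7%.
- For an event that does not end treatment, a table confined to completers would give 8.8% (n = 40) or 16.8% (n = 20).

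So even a clean record would be imprecise, which is why each count needs its denominator and interval.

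**Two limits of the data.**
- Section 4.4.2 continues self-report only. The HRSD is researcher-rated, so no HRSD or suicide-item score is planned after discontinuation.
- Progesterone is handed out at visit 6, which is also the last scheduled mood rating (Table 1). No scheduled rating covers the progesterone week, although the adverse event reporting period does.

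**Who is discontinued.** The Clinical Assessments text in sections 3.1 and 6 discontinues a woman who develops severe depressive symptoms and gives suicidal ideation as an example. Sections 4.4.1 and 8.5 respond to suicidal thoughts with repeat assessment over three days, and discontinue on plans or intent or on the woman's own concern about continuing. The triggers differ, and they decide who leaves the analysis.

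**The case against.** The case on the other side is that safety is handled in section 8. All events are questioned for and recorded, all are to be reported to the FDA, withdrawals go to the IRB, and the investigator must assess serious events, retention and the balance of risk and benefit across the study. Section 7.3 gives a brain-function rationale and never says it governs adverse events. This is a small uncontrolled pilot. The protocol expects less attrition than the under-20% seen in a 12-month trial, and without placebo, mood worsening in depressed women cannot be attributed to estradiol.

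Much of this stands, and it rules out three stronger readings that a reader might infer.
- That harms vanish from the trial. They do not: they are recorded, reported and, for serious events, reviewed in aggregate.
- That the compliant set yields a biased harm rate, for example 0/40 against some positive count in 50. Treatment-ending events among women who did not end treatment are zero by definition, no such rate is planned, and the number of leavers with harm is not given.
- That the tables would measure harm caused by estradiol. With no placebo group they cannot.

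The objection does not supply what is missing. Nothing in section 8 requires a table in the study's results, by group and over all treated women. Section 8.6.1 lists the independent monitoring board as N/A, so no board report would fill the gap.

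**Conclusion.** The point holds as a gap in planned reporting. It is certain that 3.4 is empty, that section 7 has no adverse event or discontinuation summary, and that post-discontinuation ratings have no stated use. It is probable, not certain, that 7.3 excludes women stopped for harm, because protocol-compliant is undefined. The number affected cannot be derived from the documents; the 0 to 10 range rests on the attrition allowance being met exactly. The gap does not undermine the design or the imaging aims, but it should be closed before analysis because the data are already being collected.

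**What to change.** Replace N/A in 3.4 and add to 7.2 and 7.3:

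- *Safety set:* every woman who applied at least one estradiol patch. The compliant-only rule in 7.3 does not apply to this set.
- *Tables by group, with denominators and exact 95% confidence intervals:* adverse events, serious adverse events, and discontinuations with reasons.
- *Mood:* describe change from visit 3 in the HRSD, including the suicide item, and in the self-report scales. Show on-treatment ratings separately from those collected after discontinuation.
- *Stated limits:* no HRSD is planned after discontinuation, no scheduled mood rating covers the progesterone week, and the tables are descriptive.

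Define protocol-compliant in 7.3, and say whether a woman withdrawn under the protocol's own rules counts as compliant. Reconcile the discontinuation triggers in sections 3.1 and 6 with those in 4.4.1 and 8.5. Which trigger applies is a clinical decision for the investigators.

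The cost is some wording and a few descriptive tables from data already collected, with no new visits or assays. The downside is that reported tolerability may look less favourable.
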